- Use one of the attachment buttons in this section or under the Additional Information section to include supplemental information with your application. During the document upload process, you will be able to provide a brief description of the attachment.

Background

Include a brief review of existing literature in the area of your research. You should identify gaps in knowledge that should be addressed and explain how your research will address those gaps or contribute to existing knowledge in this area. For interventional research, search PubMed and ClinicalTrials.gov for duplicative ongoing and completed trials with same condition and intervention(s).

Social support is well documented as having a significant, independent relationship with T2DM self-care. In rural environments social networks and social support may play a different role than in urban environments. In older rural-dwelling adults diagnosed with chronic disease have worse social function and emotional well-being than older adults living in urban areas. The proposed research will provide insight into the impact of social support within community- and individual-level social networks. Historically, social support has been defined by relational characteristics such as marital status and perceived social support. Yet, these characteristics do not adequately explain how relationships influence social support, health behaviors, and health outcomes. Social network analysis (SNA) is characterized as the examination and interpretation of relational connections. This approach can be used to map social networks and understand relationships between individuals as it pertains to social support. The preliminary data used for this K01 application was collected from the BRFSS where data is self-reported and its accuracy cannot be confirmed, and a dataset where social support was not the primary objective of the study and there was a small sample size all older adults. Yet, there remains a body of literature that substantiates the influence of social support on T2DM self-care and the disproportionate burden of T2DM in older adults. The proposed research will provide a comprehensive overview of the role of social support and how to leverage this support in a rural community.

Objectives

List your research objectives. Please include a summary of intended research objectives in the box below.

Describe and evaluate the impact of social support on self-care and clinical outcomes in rural-dwelling older adults with T2DM through semi-structured interviews (Aim 2). Test the feasibility and preliminary effectiveness of a 6-week intervention administered by the research coordinator targeting rural-dwelling older adults with T2DM (seed) and an individual within their social support network (alter) (Aim 3).

Study Design

Describe and explain the study design (e.g., observational, secondary analysis, single/double blind, parallel, crossover, deception, etc.).

- *Clinical Research*: Indicate whether subjects will be randomized and whether subjects will receive any placebo.
- *Community-Based Participatory Research*: If you are conducting [community-based participatory research \(CBPR\)](#), describe strategies for involvement of community members in the design and implementation of the study, and dissemination of results from the study.
- *Qualitative research*: Indicate ranges where flexibility is needed, if a fixed interview transcript is not available, describe interview topics including the most sensitive potential questions.
- *Research Repositories*: If the purpose of this submission is to establish a Research Repository (bank, registry) and the material you plan to collect is already available from a commercial supplier, clinical lab, or established IRB approved research repository, provide scientific justification for establishing an additional repository collecting duplicate material. Describe the repository design and operating procedures. For relevant information to include, see the [UK Research Biospecimen Bank Guidance](#) or the [UK Research Registry Guidance](#).

The study consists of two aims: For Aim 2, A mixed-methods approach will be used to map social networks of older adults and assess their perceived social support from members of their social network and determine its influence on self-care and clinical outcomes. In addition, through Aim 3, social networks will also be assessed to identify an individual within each older adult's network who can best facilitate optimal self-care. This person will form a dyad with the older adult to participate in a multilevel intervention which includes: gauging the feasibility of using community health workers identified via social network analysis, to conduct self-care sessions in rural communities and feasibility of seed-alter dyads to provide social support that improves self-care in older adults.

Attachments

Subject Recruitment Methods & Advertising

Describe how the study team will identify and recruit subjects. Please consider the following items and provide additional information as needed so that the IRB can follow each step of the recruitment process.

- How will the study team identify potential participants?
- Who will first contact the potential subjects, and how?
- Will you use advertisements? If so, how will you distribute those?
- How and where will the research team meet with potential participants?
- If applicable, describe proposed outreach programs for recruiting women, minorities, or disparate populations.
- How you will minimize undue influence in recruitment?
- Attach copies of all recruiting and advertising materials (emails, verbal scripts, flyers, posts, messages, etc.).

For additional information on recruiting and advertising:

- [IRB Application Instructions - Advertisements](#)
- [PI Guide to Identification and Recruitment of Human Subjects for Research](#)

Seeds: Older adults will be primarily recruited from the University of Kentucky (UK) Center of Excellence in Rural Health clinic. Additional recruitment locations will include UK's Community and Family Medicine, Internal Medicine, Endocrinology, and Geriatric outpatient clinics as well as with community organizations associated with the Barren River Area Development District (BRADD). [name], MD will identify eligible participants based on age (≥ 55 years) and diagnosis of diabetes and send out recruitment letters to these participants providing an overview of the study and contact information. Additionally, our providers [name] and [name] have agreed to allow mailers to be sent to their eligible patients. Recruitment flyers will also be posted at all clinics involved in recruitment efforts and study information will be available via UK Center for Clinical and Translational Science website that is designed to assist investigators recruit eligible study participants.

Alters: As a result of social network analysis of individual older adults (seeds) in Aim 1, a member of the social network (alter) will be identified to participate in as a seed-alter dyad ($N=262$) social support intervention. Contact information for alters will be provided by the seed during Aim 1. Eligible alters will be mailed a recruitment letter from the principal investigator that provides an overview of the study and contact information. The seed and alter must be consented to participate in the intervention.

Seed: Recruitment letters signed by a primary care physician will be sent to eligible participants providing an overview of the study and contact information. Recruitment flyers will also be posted at the Center of Excellence in Rural Health and study information will be available via UK Center for Clinical and Translational Science website that is designed to assist investigators recruit eligible study participants.

Alter: Eligible alters will be mailed a recruitment letter from the principal investigator that provides an overview of the study and contact information.

Attachments

Attach Type	File Name
Advertising	University of Kentucky Research-3.pdf
Advertising	Social Network Analysis and Social Support Intervention.pdf
Advertising	University of Kentucky Research-2.pdf
Advertising	SNA_CMRecruitment.pdf
Advertising	SNA.EmailRecruitment.pdf
Advertising	SNA.GENFlyer.pdf
Advertising	Flyer (1).pdf
Advertising	Flyer_Highlighted.pdf

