Information to be recorded includes: age, sex, race/ethnicity, marital status. Identity verification: prior to consent, all participants will be asked to complete a verification survey through RedCap detailing their name, birthday, best contact number, and best email address. If potential participants complete the verification survey but do not end up enrolling in the study, their verification survey data will be promptly removed from the studies RedCap. Health status: comorbidities (quantified using Charlson Comorbidity Index). Social support: The Medical Outcomes Study (MOS) Social Support Survey uses a 5-point Likert scale response to their perceived social support with a corresponding value to assess perceived social support. Primary outcome variables. Clinical outcomes: Hemoglobin A1c. Secondary outcome variables. Self-care: The Diabetes Self-Management Questionnaire is a 16-item questionnaire to assess self-care activities activity associated with glycemic control and has an internal consistency of 0.84. Medication adherence: Brooks Medication Adherence Scale is a 6-item scale with a reliability coefficient >0.69 and is sensitive to changes in adherence due to intervention. Quality of life—EuroQol-5D (EQ-5D) is validated measure of 5 dimensions of health-related quality of life including mobility, self-care, usual activities, pain/discomfort, and anxiety/depression.

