↳ ResearchProcedures	Agenda- DEEPTraining.pdf	DEEP Training Modules Agenda	0.591	acmi238	7/17/2018 11:09:28 AM
↳ ImpairedConsent	Form_T_1Ai STUDY 2 Rural Dwelling Older Adults with T2DM.doc	Form T Study 2	0.085	acmi238	7/9/2018 9:16:20 AM

Protocol Changes

No Changes

There are no recorded changes tracked for this protocol.

Study Personnel Changes:

Status	PPIdentify	ProtocolID	PersonID	RoleInProtocol	IsContact	LastName	FirstName	Email	DeptCode	RoomBuilding	SpeedSort	PhoneNum	DeptDesc	AuthorizedConsent	ResponsibilityInProject	Degree	Rank	StatusFlag	IsRemoved	ModBy	ModDate	SFI	IsPIRN	MiddleName
Deleted	874804	97093	12645778	DP	N	[name]	[contact]						Y		Study Coordinator	MSPH	P	Y	bism233	0/10/2024 11:18:47 AM	N		

No comments

Statistical Analysis Plan 45777

Study Overview: Data was collected at three-time points baseline, 6 months, and 12 months to assess the effect of intervention on primary and secondary outcome variables.

Descriptive statistics, change in mean score and correlation analysis was done. Sample characteristics were calculated for overall sample. Continuous variables were reported as mean and standard deviation while categorical variables were reported as frequency and percent for each time points. Pearson correlation analysis was done to assess the strength of relationship across difference time points between primary and secondary outcomes variables. Linear mixed effect model was done to analyze the change in primary outcome variable and secondary outcome variables mean score over time. Missing values were excluded from the analysis. Statistical Analysis was done in SAS v 9.4. A p-values of <0.05 was statistically significant.

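### Aim 3 sets out to test feasibility, but the SAP contains no feasibility analysis and yields no feasibility estimate

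*Combined protocol and SAP*

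**What the plan says.** Under Objectives, Aim 3 is worded "Test the feasibility and preliminary effectiveness of a 6-week intervention", so feasibility comes first and effectiveness is called preliminary. Study Design splits feasibility into two questions. One is "gauging the feasibility of using community health workers identified via social network analysis" to run the self-care sessions. The other is the "feasibility of seed-alter dyads to provide social support that improves self-care in older adults".

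The outcomes are listed under Records, Privacy, and Confidentiality. The primary outcome is HbA1c ("Primary outcome variables. Clinical outcomes: Hemoglobin A1c"). The secondary list begins "Secondary outcome variables. Self-care: The Diabetes Self-Management Questionnaire is a 16-item questionnaire" and goes on to medication adherence and quality of life.

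The SAP (Statistical Analysis Plan 45777) says data were collected at baseline, 6 and 12 months "to assess the effect of intervention on primary and secondary outcome variables". It lists sample characteristics, means with standard deviations, frequencies with percentages at each time point, and Pearson correlations among outcomes. For the model it says: "Linear mixed effect model was done to analyze the change in primary outcome variable and secondary outcome variables mean score over time". Missing values are excluded and significance is set at 0.05.

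Other parts of the protocol plan data that bear on feasibility. The attachment lists include a feasibility follow-up interview packet and post-intervention questions. Data Collection & Research Materials describes a three-question survey after the intervention. Records, Privacy, and Confidentiality describes a fidelity manual and random audits of community health worker activity.

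**The concern.** Aim 3 has two purposes, and only one has a planned analysis. A change in mean HbA1c or in a questionnaire score does not show whether a seed's chosen alter agrees to take part, whether the pair attends six sessions of 1.5 hours and the 6-month booster, or whether both return for assessment at 12 months. Nor does the lack of a change show that these things failed. If the report follows the SAP alone, a reader who wants to know whether the dyad approach can be delivered to rural older adults will find no rate, no denominator and no interval.

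**Working it through.** **Step 1. Objectives against analyses.**

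| Stated feasibility question | Quantity that would answer it | In the SAP? |
|---|---|---|
| Community health workers run sessions (Study Design) | Sessions delivered by such workers; fidelity-audit results | No |
| Dyads provide support (Study Design) | Seeds with a consenting eligible alter; attendance; return at 6 and 12 months | No |
| Dyad support improves self-care (same sentence) | Change in self-care score | Yes, through the mixed model |

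The SAP's analyses concern sample characteristics and the named outcomes. It does not mention feasibility, consent, dyad formation, attendance, retention, fidelity or acceptability, and it includes no qualitative analysis.

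**Step 2. Planned feasibility data against analyses.** The interview packet, post-intervention questions and fidelity audits each appear in the protocol. No supplied text says how any of them is summarised or judged. The contents of the attachments are not visible, so this finding is limited to the SAP and protocol text.

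**Step 3. Which question the data can answer.** Study Design has community health workers conducting sessions. Objectives and Research Procedures assign the sessions to the research coordinator, and Data Collection & Research Materials assigns them to the research assistant. These passages need to be reconciled before the community health worker question can be given a measure.

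**Step 4. The denominator.** Project Information gives a maximum of 262 human subjects. The planned enrolment table in Subject Demographics sums to the same figure: 1 + 1 + 1 + 1 + 2 + 125 + 131 = 262. That points to persons, hence 262 / 2 = 131 dyads if everyone is paired. Yet the study population and recruitment text attach N=262 to the dyad, which would mean 2 × 262 = 524 people, twice the stated maximum.

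**Step 5. Would the estimates be informative?** The plan states no feasibility figure, so there is none to reproduce. As an illustration, take x successes among n dyads and the exact (Clopper-Pearson) 95% interval:

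- lower limit = 0.025 quantile of Beta(x, n − x + 1)
- upper limit = 0.975 quantile of Beta(x + 1, n − x)

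| Assumed rate | n = 131: x, 95% CI | n = 262: x, 95% CI |
|---|---|---|
| 50% | 66, 41.5% to 59.2% | 131, 43.8% to 56.2% |
| 70% | 92, 61.6% to 77.9% | 183, 63.9% to 75.3% |
| 80% | 105, 72.3% to 86.6% | 210, 74.8% to 84.8% |
| 90% | 118, 83.6% to 94.6% | 236, 85.8% to 93.4% |

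The rates are assumptions; the documents give none. Across this range a dyad-level rate would be known to within about 9 percentage points either way with 131 dyads, and about 6 with 262. The enrolment reached may be lower than the maximum, which would widen these intervals.

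**The case against.** The strongest reply is that feasibility has not been neglected. The interview packet, post-intervention questions and fidelity audits are planned, and feasibility may be meant largely as a qualitative question. Frequencies at each time point would also hint at retention, and self-care, which forms part of the second feasibility question, is modelled over time. All of this is fair. It means one cannot say that the study collects nothing on feasibility, or that the aim must go unanswered. What remains is that none of the planned feasibility data has a stated analysis. The SAP's frequencies also have no consented or enrolled denominator, so they cannot give dyad-formation or attendance rates.

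A reader might also infer two stronger points that the documents do not support.

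- *That excluding missing values removes non-attenders.* The exclusion concerns values in the outcome analysis. A mixed model that drops a missing visit can still use the same seed's other visits. HbA1c is abstracted from medical records, so a seed who skipped sessions may still have a value. The rule also does not prevent anyone from counting who attended.
- *That feasibility would be decided on HbA1c p-values.* The SAP says nothing of the kind. Its stated purpose is the effect on outcomes, and it draws no feasibility conclusion.

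A further objection concerns timing and recoverability. The SAP is written in the past tense and the anticipated end date was 3/31/2024, so measures added now may be post hoc. Recruitment used letters, flyers and a website, and verification data from people who do not enrol are deleted, so the number of seeds approached may not exist. No attendance log is described. These points stand, and they limit what the fix can ask for.

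**Conclusion.** The concern holds in a limited form: feasibility is a named purpose of Aim 3, and the SAP has no analysis that estimates it. The gap lies in the analysis plan and not wholly in data collection. It does not undermine the outcome analyses. Its size is one of Aim 3's two stated purposes left without a planned quantitative result, where rates with intervals of useful width could be reported (72.3% to 86.6% for 131 dyads at an assumed 80%). This rests on the supplied text being complete on the point, since the attachments' contents are unseen, and the precision figures rest on full enrolment and assumed rates. It is a cheap improvement that should be made.

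**What to change.** Add a descriptive feasibility section to the SAP, with exact 95% intervals and consented seeds or enrolled dyads as the denominator:

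- seeds with a consenting eligible alter, out of consented seeds;
- dyads attending all 6 sessions, at least 5 of 6, and the booster, where attendance was recorded;
- seeds and alters completing the 6- and 12-month study assessments, reported separately from whether an HbA1c value exists in the medical record;
- a summary of the fidelity audits;
- a short plan for analysing the feasibility interviews and post-intervention questions.

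Report seeds consenting out of letters mailed only if that count exists. State whether 262 means persons (131 dyads) or dyads. Reconcile the passages on who delivers sessions, and say which Study Design question, community health workers or dyads, the data can answer. Base the feasibility conclusion on these measures, and label them post hoc if analysis has already begun. Go/no-go thresholds are optional, because the supplied text describes no follow-on trial and values chosen now would probably be post hoc.

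The cost is some SAP text and a little more tabulation. The downside is that some rates may be unfavourable and others may not be recoverable; where a rate cannot be recovered, say so.

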- Describe all sources or methods for obtaining research materials about or from living individuals (such as specimens, records, surveys, interviews, participant observation, etc.), and explain why this information is needed to conduct the study.
- For each source or method described, please list or attach all data to be collected (such as genetic information, interview scripts, survey tools, data collection forms for existing data, etc.).
- If you will conduct a record or chart review, list the beginning and end dates of the records you will view.

Data collection will be semi-structured interviews that will be audio-recorded, de-identified and transcribed verbatim. A semi-structured interview guide will be adapted from a previously published intervention assessing social networks and health behavior as well as informed by preliminary data and expert opinion of my team of mentors and advisors. Interviews will include two broad general questions asking "who" to map the social network of older rural-dwelling adults diagnosed with T2DM and "how" members of the social network provide social support; using open-ended questions to elicit maximal information with minimal bias. Interview questions will explore the follow domains (although additional domains may be identified during interview development): size and structure of social network; resources available through social network; and beliefs of those in social network regarding T2DM knowledge and self-care. A three question survey will be discharged post intervention to further assess community members perception of community leaders and the tentative role they could play in diabetes education.

For Aim 3, consent will be collected one of two ways. Using a phone script to initiate the informed consent process, potential participants have the option to complete consent using (1) a physical consent form (2) an electronic consent form using REDCap. After consent has been obtained, a research assistant (RA) will collect demographics, T2DM and geriatric risk assessment data, and baseline clinical outcomes (weight, height, pulse, systolic blood pressure, diastolic blood pressure, LDL, and Hemoglobin A1C levels) will be abstracted from electronic medical records of all seeds. The RA will administer the education sessions, which will ideally occur weekly. Once participants have completed the six education sessions, a summer SPARKS student will mail out an optional survey assessing social needs, as well as a self addressed return envelope should the participant choose to complete the survey. At the 6- and 12-month study visits the RA will obtain clinical outcomes and T2DM and geriatric assessments from all seeds. Alters will complete assessments on T2DM knowledge and social support at baseline, 6 and 12 months. These time points have been chosen because this provides enough time for participants to implement behavior changes that can result in meaningful changes in geriatric- and T2DM- specific assessments. Additionally, relevant clinical measures, specifically blood pressure, HbA1c, and lipid panel are clinically relevant for 6 months. Dyads will be given a booster session provided by RA at 6 months. These modules have been chosen because they reinforce understanding of what T2DM looks like on an individual level, practical ways to manage T2DM, and how to support those with T2DM. All self-care sessions and study visits will be held at designated community organizations—churches, senior centers, schools, and community centers. In the event that any of these assessments reflect a risk for a geriatric syndrome, the seed-alter dyad will be asked to contact the seed's primary care provider (PCP), the PCP will be notified via research note the seed's electronic medical record, and [name] will follow up with all PCPs that are notified. At the 6-month study visit older adults will be asked to participate in a semi-structured interview as a follow up to the interview provided in Aim 2. The purpose of this interview to it

examine if the participants social network, social support, and information provided via social networks changed over time and if there is a relationship with their self-care adherence since baseline.

Attachments

Attach Type	File Name
DataCollection	E.J_Social Needs Questionnaire.docx
DataCollection	Study 2 Aim 3 PATIENT Assessment Tool.pdf
DataCollection	Evaluation survey questions.pdf
DataCollection	Evaluation survey questions_Clean.docx
DataCollection	Study 2 Aim 3 PATIENT Assessment Tool_Clean.pdf
DataCollection	75339_DataCollection_237366.pdf
DataCollection	75339_DataCollection_237366.pdf
DataCollection	Study 2 Aim 2_Community Networks Interview Guide_10 28 20.pdf
DataCollection	Charlson Comorbidity.pdf
DataCollection	Study 2 Aim 3 PATIENT Assessment Tool.pdf
DataCollection	Study 2 Aim 3 ALTER Assessment Tool.pdf
DataCollection	Orsmond and Cohn Feasibility interview packet.pdf
DataCollection	Study 2 Aim 3 PATIENT Assessment Tool.pdf
DataCollection	Study 2 Post-Intervention Questions.pdf
DataCollection	Study 2 Aim 3 PATIENT Assessment Tool.pdf

Resources

Describe the availability of the resources and adequacy of the facilities that you will use to perform the research. Such resources may include:

- Staffing and personnel, in terms of availability, number, expertise, and experience;
- Computer or other technological resources, mobile or otherwise, required or created during the conduct of the research;
- Psychological, social, or medical services, including equipment needed to protect subjects, medical monitoring, ancillary care, or counseling or social support services that may be required because of research participation;
- Resources for communication with subjects, such as language translation/interpretation services.

All self-care sessions and study visits will be held at designated community organizations-- churches, senior centers, schools and community centers.

Potential Risks & Benefits

Risks

- Describe any potential risks – including physical, psychological, social, legal, ability to re-identify subjects, or other risks. Assess the seriousness and likelihood of each risk.
- Which risks may affect a subject's willingness to participate in the study?
- Describe likely adverse effects of drugs, biologics, devices or procedures participants may encounter while in the study.
- *Qualitative research* - describe ethical issues that could arise while conducting research in the field and strategies you may use to handle those situations.
- Describe any steps to mitigate these risks.

Benefits

- Describe potential direct benefits to study participants – including diagnostic or therapeutic, physical, psychological or emotional, learning benefits. This cannot include incentives or payments.
- State if there are no direct benefits.
- Describe potential benefits to society and/or general knowledge to be gained.

Describe why potential benefits are reasonable in relation to potential risks. If applicable, justify why risks to vulnerable subjects are reasonable to potential benefits.

Potential Risk to participants are minimal as data collection involves: (1) confirmation of type 2 diabetes diagnosis using billing data and electronic medical records, (2) semi-structured interviews, (3) completion of questionnaires, and (4) electronic chart review (seeds) and collection of data in the form of validated questionnaires for both seeds and alters. Risks include potential loss of confidentiality. Efforts to reduce loss of confidentiality are outlined in the Confidentiality section.

No direct benefits are expected for the seeds and alters who participate in the semi-structured interviews. There is the potential benefit that may be experienced as the result of the intervention such as feelings of increased social support, improved clinical outcomes associated with T2DM diagnosis, and self-management education gained by both seeds and alters. Furthermore, recognition by study staff of significant stress or emotional strain in a seed or alter during an interview may prompt referral to a primary care physician or other health care provider who may provide clinical care to these subjects. The risks posed to the subjects in this study are minimal and are outweighed by the knowledge to be gained. Taken together, findings from this work will directly inform community-based research; help clinicians, policy-makers and members of social networks facilitate adherence to T2DM self-care in rural dwelling older

adults; and reveal targets to improve care for rural dwelling older adults living with complex chronic disease.

Available Alternative Opportunities/Treatments

Describe alternative treatments or opportunities that might be available to those who choose not to participate in the study, and which offer the subject equal or greater advantages. If applicable, this should include a discussion of the current standard of care treatment(s).

Should subjects choose not to participate in the study, there is no alternative treatment offered. Subjects will be encouraged to seek standard treatment of care from their provider.

[Back to Top](#)

Records, Privacy, and Confidentiality

Specify where the data and/or specimens will be stored and how the researcher will ensure the privacy and confidentiality of both. Specify who will have access to the data/specimens and why they need access.

Describe how data will be managed after the study is complete:

- If data/specimens will be maintained, specify whether identifiers will be removed from the maintained information/material.
- If identifiers will not be removed, provide justification for retaining them and describe how you will protect confidentiality.
- If the data/specimens will be destroyed, verify that this will not violate [retention policies](#) and will adhere to applicable facility requirements.

If this study will use de-identified data from another source, describe what measures will be taken to ensure that subject identifiers are not given to the investigator.

If applicable, describe procedures for sharing data/specimens with collaborators not affiliated with UK.

For additional considerations:

[Return of Research Results or Incidental Research Findings](#)

[HIPAA policies](#)

[FERPA policies](#)

[Procedures for Transfer agreements](#)

[Information regarding multi-site studies](#)

[NIH Genomic Data Sharing \(GDS\) Policy](#)

[Digital Data](#)

Sources of research material include Electronic Health Records and medical billing information.

Information to be recorded includes: age, sex, race/ethnicity, marital status. Identity verification: prior to consent, all participants will be asked to complete a verification survey through RedCap detailing their name, birthday, best contact number, and best email address. If potential participants complete the verification survey but do not end up enrolling in the study, their verification survey data will be promptly removed from the studies RedCap. Health status: comorbidities (quantified using Charlson Comorbidity Index). Social support: The Medical Outcomes Study (MOS) Social Support Survey uses a 5-point Likert scale response to their perceived social support with a corresponding value to assess perceived social support. Primary outcome variables. Clinical outcomes: Hemoglobin A1c. Secondary outcome variables. Self-care: The Diabetes Self-Management Questionnaire is a 16-item questionnaire to assess self-care activities activity associated with glycemic control and has an internal consistency of 0.84. Medication adherence: Brooks Medication Adherence Scale is a 6-item scale with a reliability coefficient >0.69 and is sensitive to changes in adherence due to intervention. Quality of life—EuroQol-5D (EQ-5D) is validated measure of 5 dimensions of health-related quality of life including mobility, self-care, usual activities, pain/discomfort, and anxiety/depression.

Seed characteristics: age, gender, race/ethnicity, education, employment status. Alter characteristics: age, gender, race/ethnicity, education, relationship to the participant. Social support: The Medical Outcomes Study (MOS) Social Support Survey uses a 5-point Likert scale response to their perceived social support with a corresponding value to assess perceived social support. Health status: comorbidities will be quantified using Charlson Comorbidity Index. Geriatric syndrome risk assessments: Cognitive impairment: Montreal Cognitive Assessment-Basic (MoCA-B) was developed to screen for mild cognitive impairment in elderly adults with low education and varying literacy and has a reliability coefficient of 0.91. Nutritional status: Mini-Nutritional Assessment (MNA) was designed and validated to provide a nutritional status in older adults patients in outpatient clinics, in hospitals, and nursing homes. The MNA measures adequate nutritional status, protein-calorie malnutrition, and risk of malnutrition. Frailty: Fried Frailty Index measures five domains of frailty based the definition provided by Fried et al. (2001): exhaustion, unintentional weight loss, low activity, slow walk, and grip strength in the elderly. Physical function: Lawton's Instrumental Activities for Daily Living Scale which evaluates the ability to independently use the toilet, feed, dress, groom, bathe and perform physical ambulation. Fall risk: Get Up and Go Test89 requires rising from the chair and walking a short distance and walking back to the chair. The observer is asked to score the performance from 1 (normal—no evidence of fall risk) to 5 (severely abnormal—participant appeared at risk for fall during the assessment). Depression: Geriatric Depression Scale is sensitive to those suffering from mild cognitive impairment and physical illness. Quality of life: EuroQol-5D (EQ-5D) is validated measure of 5 dimensions of health-related quality of life including mobility, self-care, usual activities, pain/discomfort, and anxiety/depression. The EQ-5D also includes a Visual Analogue Scale by which respondents can report their perceived health status ranging from 0 (the worst possible health) to 100 (the best possible health).

Data collected from validated questionnaires and clinical outcomes (abstracted from the electronic medical records) will be stored in

RedCap. All original data collection forms will only include assigned participant study IDs that were assigned at enrollment and stored in a locked cabinet, in a locked office in the UK Center for Health Services Research. Study participants who are older adults (seeds) will be asked to complete validated geriatric syndrome risk assessments at baseline, 6 and 12 months. During those assessments if it is determined that a seed is at-risk for a geriatric syndrome, a letter will be sent to their primary care provider alerting them of our finding. In that event, we will also recommend the seed to contact their primary care provider for further assessment. Additionally, a board-certified geriatrician ([name]) included as an advisor on this grant, will follow-up with primary care providers who have been contacted as a result of our study findings to ensure that study participants receive appropriate standard of care for any identified geriatric syndromes. Additionally, to maintain fidelity among CHWs a structured manual will be created to carefully track fidelity to the protocol. The principal investigator along with the advisor in community health worker training ([name]) will conduct random audits of CHW activities by visiting with them or calling participants to check on interaction and advice given.

This study will collect qualitative and quantitative data with minimal risk of requiring medical attention to the research participant. The semi-structured interviews will not inquire about personal health information of research participants. Research participants' audio files will be saved on an encrypted device and the information provided will be de-identified and transcribed by a member of the research team. All audio files will also be saved on the UK Center for Health Services Research password protected server. We do not anticipate that semi-structured interviews will be distressing, however in order to minimize risks to seeds and alters, the research assistant will be carefully trained by both Drs. [name] and [name] in interview techniques. In the unlikely event that a participant becomes overwhelmed or prefers not to continue the interview for any reason, the research assistant will be instructed to end the interview.

All staff involved in this proposal will have completed requisite training in the protection of human subjects as delineated by the Institutional Review Board of the University of Kentucky (UK). All study documentation will be stored in a locked area, accessible only to the PI, RA and other designated study staff. All interviews will be audio-recorded with the permission of the participant. The audio files will be transcribed using a trained transcriptionist within UK's Center for Health Services Research. Additionally, all desktop, laptop, and handheld devices are encrypted according to UK policies. Participants will be assigned a numerical code for identification in the files. Names and other identifiers will be kept in separate encrypted files accessible only to the investigators.

UK IRB policies state that IRB-related research records must be retained for a minimum of 6 years after study closure. Do you confirm that you will retain all IRB-related records for a minimum of 6 years after study closure?

Yes No

Payment

Describe the incentives (monetary or other) being offered to subjects for their participation. If monetary compensation is offered, indicate the amount and describe the terms and schedule of payment. Please review [this guidance](#) for more information on payments to subjects, including restrictions and expectations.

Initial interview with Seeds and Alters: Participants will receive \$20 for completing the interview and validated surveys. Both the seed and alter will receive \$15 for each study visit completed at baseline, 6 and 12 months.

Costs to Subjects

Include a list of services and/or tests that will not be paid for by the sponsor and/or the study (e.g., MRI, HIV). Keep in mind that a subject will not know what is "standard" – and thus not covered by the sponsor/study – unless you tell them.

There are no cost to subjects other than the time required to attend the sessions.

Data and Safety Monitoring

The IRB requires review and approval of data and safety monitoring plans for greater than minimal risk research or NIH-funded/FDA-regulated clinical investigations.

- If you are conducting greater than minimal risk research, or your clinical investigation is NIH-funded, describe your Data and Safety Monitoring Plan (DSMP). [Click here for additional guidance on developing a Data and Safety Monitoring Plan.](#)
